10.5. Appendix 5: Data Display Standards & Handling Conventions

10.5.1. Study Treatment & Sub-group Display Descriptors

Treatment Group Descriptions			
IVWRS		Data Displays for Reporting	
Code	Description	Description	Order [1]
A	Dapro	Dapro	1
B	Darbepoetin alfa	Darbe	2
--	--	Total	3

NOTES:

- Order represents treatments being presented in TFL, as appropriate.

10.5.2. Baseline Definition & Derivations

10.5.2.1. Baseline Definitions

For all endpoints (except as noted) the baseline value will be the latest non-missing pre-dose assessment on or before the randomization date. This is generally expected to be the pre-dose value from the Day 1 visit, although such values may be missing.

Parameter	Study Assessments Considered As Baseline			Baseline Used in Data Display
	Screen Week -8	Run-in Week -4	Day 1 (Pre-Dose)	
Efficacy				
Hgb			X	Randomization Date
Iron parameters			X	Randomization Date
Safety				
BP parameters, HR and weight ¹			X	Randomization Date
Lipid parameters, renal function parameters, clinical chemistry, hematology, other laboratory and hepatobiliary (liver) tests			X	Randomization Date

Parameter	Study Assessments Considered As Baseline			Baseline Used in Data Display
	Screen Week -8	Run-in Week -4	Day 1 (Pre-Dose)	
PRO				
SF-36 domain and component scores			X	Randomization Date
EQ-5D-5L & VAS			X	Randomization Date
PGI-S			X	Randomization Date
CKD-AQ			X	Randomization Date
WPAI-ANS-CPV			X	Randomization Date

[1]: For subjects who start dialysis during the study, the baseline vital sign values will be used as baseline values for pre- and post- dialysis vital sign displays and baseline weight will be used as the baseline dry weight value.

NOTES:

- Unless otherwise stated, the mean of replicate assessments at any given time point will be used as the value for that time point.

10.5.2.2. Derivations and Handling of Missing Baseline Data

Change from Baseline

Definition	Reporting Details
Change from Baseline	= Post-Baseline Visit Value – Baseline

NOTES:

- Unless otherwise specified, the baseline definitions specified in Section 10.5.2 Baseline Definitions will be used for derivations for endpoints / parameters and indicated on summaries and listings.
- Unless otherwise stated, if baseline data is missing no derivation will be performed and the change from baseline value will be set to missing.
- The baseline definition will be footnoted on all change from baseline displays.

Percent Change from Baseline

Lipid parameters will be log-transformed and the percent change from baseline will be reported. Other endpoints may also be log-transformed if deemed appropriate.

To calculate a geometric mean for baseline measurement or at a specified timepoint, the following steps are used:

1. Log-transform the data points
2. Calculate the mean and standard error (SE) of the log-transformed data
3. Exponentiate the mean, (if required, the mean – SE, mean + SE) and the endpoints of the confidence interval back to the original scale in order to obtain the geometric

mean, (the geometric mean – SE, the geometric mean + SE) and the confidence interval for the geometric mean.

4. Coefficient of variation will be calculated as

$$CV = \sqrt{\exp(\text{Var}_{\log\text{scale}}) - 1} \times 100\%$$

To calculate a geometric mean for the ratio of a specific timepoint to baseline (expressed as a percent change from baseline), the following steps are used:

1. Log-transform the data at both the baseline and the specified timepoint
2. For each subject, calculate a change from baseline using the log-transformed data
3. Calculate the mean and standard error (SE) of change from baseline using the log-transformed data
4. Exponentiate the mean, (if required, the mean – SE, the mean + SE), back to the original scale and then subtract 1, then multiply everything by 100% in order to express the geometric mean, (the geometric mean – SE, the geometric mean + SE) as the percent change from baseline.

So, geometric mean for percent change from baseline =

$$[\text{Exp}(\sum \{ \log(\text{value at specified time point}_i) - \log(\text{baseline value}_i) \} / n) - 1] \times 100,$$

Where i = subject, n = total number of subjects, and \sum represents the sum over all subjects.

To calculate a 95% CI of the geometric mean for the ratio of a specific timepoint to baseline (expressed as a percent change from baseline), the following steps are used:

1. Log-transform the data at both the baseline and the specified timepoint
2. For each subject, calculate a change from baseline using the log-transformed data
3. Calculate the mean and standard error (SE) of change from baseline using the log-transformed data
4. Calculate the lower and upper limits of the 95% CI of change from baseline using the log-transformed data assuming a normal distribution: Mean $\pm z(1 - \alpha/2) * \text{SE}$ (z for $\alpha=0.05$ is obtained through PROBIT function in SAS that is specified as PROBIT(0.975))
5. Exponentiate the lower and upper limits of the 95% CI, back to the original scale and then subtract 1, then multiply everything by 100% in order to express the confidence interval (CI) as the percent change from baseline.

To calculate the minimum, median and maximum for the ratio of a specific timepoint to baseline (expressed as a percent change from baseline), the following steps are used:

1. Log-transform the data at both the baseline and the specified timepoint
2. For each subject, calculate a change from baseline using the log-transformed data

3. Calculate the minimum (median and maximum) of change from baseline using the log transformed data.
4. Exponentiate the minimum (median and maximum), back to the original scale and then subtract 1, then multiply everything by 100% in order to express the minimum (median and maximum) as the percent change from baseline.

So, minimum percent change from baseline =

$$[\text{Exp}(\min \{ \log(\text{value at specified time point}_i) - \log(\text{baseline value}_i) \}) - 1] \times 100,$$

Where i = subject.

Unless otherwise specified, the baseline definitions specified in Section 10.5.2 will be used for derivations for endpoints/parameters and indicated on summaries and listings. Unless otherwise specified, if baseline data is missing, no derivation will be performed and the % change from baseline value will be set to missing. The baseline definition will be footnoted on all change from baseline displays.

10.5.3. Reporting Process & Standards

Reporting Process
Software

 • The currently supported versions of SAS software, Version 9.4 (or higher) will be used for all analyses unless otherwise specified. Additionally, R Version 3.6.2 or higher may be used for analysis and the production of graphics.
Analysis Datasets

 • Analysis datasets will be created according to clinical data interchange standards consortium (CDISC) standards: study data tabulation model (SDTM) implementation guide (IG) Version 3.1.3 with some updates from Version 3.2, Analysis data model (ADaM) IG Version 1.1, and GSK ADaM specification template. • For creation of ADaM datasets (ADCM/ADAE), the same version of dictionary datasets will be implemented for conversion from system independent (SI) to SDTM.
Generation of RTF Files

 • Rich text format (RTF) files will be generated.
Reporting Standards
General

 • The current GSK Integrated Data Standards Library (IDSL) will be applied for reporting, unless otherwise stated: 
 ○ 4.03 to 4.23: General Principles ○ 5.01 to 5.08: Principles Related to Data Listings ○ 6.01 to 6.11: Principles Related to Summary Tables ○ 7.01 to 7.13: Principles Related to Graphics
Formats

 • GSK IDSL Statistical Principles (5.03 & 6.06.3) for decimal places (DP's) will be adopted for reporting of data based on the raw data collected. • Numeric data will be reported at the precision collected on the eCRF. • The reported precision from non eCRF sources will follow the IDSL statistical principles but

Reporting Standards	
may be adjusted to a clinically interpretable number of DP's.	
Planned and Actual Time	

 • Reporting for tables, figures and formal statistical analyses: 
 • Planned time relative to randomization will be used in figures, summaries, statistical analyses and calculation of any derived parameters, unless otherwise stated. • All scheduled visits, regardless of deviation from the planned assessment times and/or scheduled visit days will be used in tables, figures and formal statistical analyses unless otherwise stated. • The derived end of treatment value (see Section 10.6.1) will also be included in displays of data by visit. • Tables presenting data values by visit will also include values from scheduled visits occurring on or before the Day 1 visit, despite the description contained in the title (e.g., post-randomization, evaluable, or on-treatment). The description in the title refers to the post-randomization values that are included in the table. • Reporting for Data Listings: 
 • Planned and actual time relative to study drug dosing will be shown in listings (Refer to IDSL Statistical Principle 5.05.1). • Unscheduled or unplanned readings will be presented within the subject's listings. • Visits outside the protocol defined time-windows (i.e. recorded as protocol deviations) will be included in listings. 	
Unscheduled Visits	

 • Unscheduled visits will not be included in summary tables, with the following exceptions: 
 • If the table includes a row for all post-baseline assessments, unscheduled visits will be included in this row. • Some Hgb endpoints will include unscheduled Hgb values (See Section 10.6.3) • Some BP endpoints will include unscheduled BP values (see Section 10.6.4) • Unscheduled visits will not be included in figures, with similar exceptions: 
 • If the figure includes a data value for all post-baseline assessments, unscheduled visits will be included in this value. 
 • Some Hgb endpoints will include unscheduled Hgb values (See Section 10.6.3) • Some BP endpoints will include unscheduled BP values (see Section 10.6.4) • All unscheduled visits will be included in listings. 	
Descriptive Summary Statistics	
Continuous Data	Refer to IDSL Statistical Principle 6.06.1
Categorical Data	N, n, frequency, %
Graphical Displays	

 • Refer to IDSL Statistical Principals 7.01 to 7.13. 	
Adjusted Means	

 • SAS option OBSMARGINS will be used to generate all adjusted mean values, e.g. LSMEANS statement in relevant SAS procedures will include the OBSMARGINS option (or OM as an abbreviation), to weight least square means coefficients of the categorical variables in the model to be proportional to those found in the input dataset. 	

10.6. Appendix 6: Derived and Transformed Data

10.6.1. General

Multiple Measurements at One Time Point

- Mean of the measurements will be calculated and used in any derivation of summary statistics but if listed, all data will be presented.
 - Triplicate BP and HR measurements are expected at certain time points (See Section 10.2.1)
- Subjects having both High and Low values for Normal Ranges at any post-baseline visits for safety parameters will be counted in both the High and Low categories of “Any visit post-baseline” row of related summary tables. This will also be applicable to relevant Potential Clinical Importance summary tables.

Randomization Date

- Date subject was randomized

Treatment Start Date

- First randomized treatment dose start date

Last Non-Zero Dose Date

- Date of last actual dose of randomized study treatment from the IP Discontinuation eCRF form.
 - The dose steps used by the dosing algorithm described in the protocol include a dose hold or a zero dose. If subjects are assigned by the algorithm to a zero dose, they do not receive randomized treatment for that period. Hence, it would be possible for a subject to complete the study, while still following the dosing algorithm, but not actually be taking any actual randomized treatment. The last non-zero dose date, then captures the latest date in the study that a subject physically took a dose of randomized treatment.
- The eCRF allows for the possibility of partial or missing dates to be recorded for the last actual dose of randomized study treatment on the IP Discontinuation form (i.e., missing day, or day and month, or day and month and year). In such a case, or in case of subjects who have a non-missing treatment start date, but are missing an IP Discontinuation form, the following conventions will be applied in order to impute a last non-zero dose date:
 - Missing day:
 - The last day of the month will be used, unless the treatment stop date also occurs in the same month; in this case, the treatment stop date will be used.
 - Missing day and month;
 - ‘31’ will be used for the day and ‘Dec’ will be used for the month, unless the treatment stop date also occurs in the same year; in this case the treatment stop date will be used.
 - Missing day, month, and year:
 - Treatment stop date will be used only for subjects who have a non-missing treatment start date.

Treatment Stop Date

- Calculated as the latest randomized treatment dose stop date for subjects who have a non-missing treatment start date. Note that this date could come from a randomized treatment exposure record with a missing or partial dose stop date if the associated dose start date for that exposure record is on or after the last non-missing randomized treatment dose stop date.
- The eCRF allows for the possibility of missing or partial dates to be recorded for the dose stop date on the study treatment form (i.e., missing day, or day and month, or day and month and year). In such a case, the following conventions will be applied in order to impute a treatment stop date:
 - Missing day:
 - The last day of the month will be used, unless the study completion or withdrawal date also occurs in the same month; in the case, the study completion or withdrawal date will be used.
 - Missing day and month:
 - '31' will be used for the day and 'Dec' will be used for the month, unless the study completion or withdrawal date also occurs in the same year; in this case, the study completion or withdrawal date will be used.
 - Missing day, month and year:
 - The study completion or withdrawal date will be used only for subjects who have a non-missing treatment start date.

End of Treatment Value

- Only defined for subjects with a non-missing treatment start date
- Hgb, iron, transfusion and PRO parameters: the latest value on or before the treatment stop date + 1 day.
- Blood pressure, central laboratory, and vital signs parameters: the latest value on or before the last non-zero dose date + 1 day.

Study Completion/Withdrawal Date

 • Date of withdrawal for subjects withdrawing (i.e., subjects who actively withdraw or are deemed lost to follow-up) from study or date of completion of study for subjects who complete the study. If the date of study withdrawal entered in the eCRF is before the last study contact date, the last study contact date will be used as the study withdrawal date for analysis. 
 • Note: Subjects who die while on study are considered as having completed the study • The eCRF allows for the possibility of missing or partial dates to be recorded for the study completion/withdrawal date on the Study Conclusion form (i.e., missing day, or day and month, or day and month and year). In such a case, or in case of subjects who are missing a Study Conclusion form, the following conventions will be applied in order to impute a study completion/withdrawal date: 
 • Missing day: 
 ▪ The last day of the month will be used, unless the last study contact date also occurs in the same month; in the case, the last study contact date will be used. • Missing day and month: 
 ▪ '31' will be used for the day and 'Dec' will be used for the month, unless the last study contact date also occurs in the same year; in this case, the last study contact date will be used. • Missing day, month and year: 
 ▪ The last study contact date will be used. • If both death and study completion/withdrawal have missing or partial dates, they will be imputed as specified (see Section 10.6.1 and Section 10.6.4). If the imputed death date is prior to the imputed study completion/withdrawal date, then the study completion/withdrawal date will use the imputed death date instead.
Planned/Actual Visit Dates

 • Planned/actual visit dates will be defined as follows: 
 ○ Week 28 date: Non-missing Week 28 visit start date (from SV domain), otherwise randomization date + 28*7 ○ Week 36 date: Non-missing Week 36 visit end date (from SV domain), otherwise randomization date + 36*7 ○ Week 52 date: Non-missing Week 52 visit end date (from SV domain), otherwise randomization date + 52*7 ○ End of Study date: Non-missing End of Study visit start date (from SV domain), otherwise the middle of the End of Study window.
Stabilization Period

 • Defined as the period between and including the Randomization date + 1 day - <Week 28 visit, using planned/actual dates.
Alternative Evaluation Period (Alt. EP)

 • Defined as the period between and including Week 28 visit – Week 36 visit, using planned/actual dates.
Evaluation Period (EP)

 Defined as the period between and including Week 28 visit – Week 52 visit, using planned/actual dates.
Maintenance Period (MP)

 Defined as the period between and including Week 28 visit – End of Study visit, using planned/actual dates.
Study Day

 Calculated as the number of days from randomization date: 
 Ref Date = Missing → Study Day = Missing Ref Date < Randomization Date → Study Day = Ref Date – Randomization Date Ref Date ≥ Randomization Date → Study Day = Ref Date – (Randomization Date) + 1
Treatment Day

 Calculated as the number of days from treatment start date: 
 Treatment Start Date = Missing → Treatment Day = Missing Ref Date < Treatment Start Date → Treatment Day = Ref Date – Treatment Start Date Ref Date ≥ Treatment Start Date → Treatment Day = Ref Date – (Treatment Start Date) + 1
Last Study Contact Date

 Latest visit date from an unscheduled visit or a clinic, telephone, designated third party, healthcare provider or medical records, other, or other contact with subject (mail, email, text, social media, etc.) visit.
Time Definitions (per GSK standard principles)

 1 week = 7 days 1 month = 30.4375 days 1 year = 365.25 days
Production of Two-Sided p-values

 The majority of the efficacy and safety analyses in this study will use one-sided 2.5% p-values to assess statistical significance. Should two-sided p-values be required for publication purposes after the study is complete, the corresponding two-sided p-values will be produced at that time.
Last Known Alive Date

 The last know alive date for a subject in the study will be defined as the latest of the following dates: 
 The date of the last visit in the clinic Last date recorded when the subject was last known alive For the non-clinic visit, the last clinic information assessment date

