10.4. Appendix 4: Treatment States and Phases

10.4.1. Treatment States

Assessments and events will be classified according to time of occurrence relative to the treatment start and stop dates and last non-zero dose date (see Section 10.6.1).

10.4.1.1. Treatment States for Hgb, Iron Parameters, Iron Use Summaries, Transfusion and PRO Data

Treatment State	Definition
Pre-Treatment	Date \leq Treatment Start Date
On-Treatment	Treatment Start Date < Date \leq Treatment Stop Date + 1 day
Post-Treatment	Date > Treatment Stop Date + 1 day
Post-Randomization	Randomization Date < Date

NOTES:

- If the treatment stop date is missing and the treatment start date is non-missing and Date > Treatment Start Date, then the assessment will be considered to be On-Treatment

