10.6.2. Study Population

10.6.2.1. Subject Disposition

Subject Disposition
Screen Failures

 Screen failures are defined as subjects who consent to participate in the clinical trial but are not

Subject Disposition

subsequently randomized.
 
 ○ At the time of screening closure, there may have been subjects who had been consented but had not been entered into the eCRF. These subjects are not included in the clinical database, but will be noted in a footnote on the Summary of Screening Status and Reasons for Screen Failures. 
 ● Any subject that consented, was entered into the eCRF, and was not randomized, but is missing a screen failure record will have the following values imputed: 
 ○ Was this subject a screen failure? = Yes ○ Reason for screen failure = Missing
Randomized Treatment Discontinuation

 ● Any randomized subject with a non-missing treatment start date that is missing an IP Discontinuation eCRF will have the following values imputed: 
 ○ Date of last dose = See Last Non-Zero Dose Date in Section 10.6.1 ○ Was the study treatment stopped permanently before the scheduled end of the treatment period? = Yes ○ Primary reason the treatment was stopped = Missing
Study Completers/Withdrawals

 ● Any randomized subject that is missing Study Conclusion eCRF will have the following values imputed: 
 ○ Date of subject completion or withdrawal? = See Study Completion/Withdrawal Date in Section 10.6.1 ○ Was the subject withdrawn from the study? = Yes ○ Primary reason for study withdrawal = Missing

Subjects Completion Status
Known Cardiovascular Endpoint Status at End of Study

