10.6.3. Efficacy

10.6.3.1. Hemoglobin Endpoints

Hemoglobin Values
Central Laboratory and HemoCue Hgb Values

 ● When source of Hgb measurement is not specified: 
 ○ For reporting purposes, central laboratory Hgb values will be used, unless otherwise specified. However, if a central laboratory Hgb value is missing, a corresponding non-missing HemoCue Hgb value will be used. This approach will

Hemoglobin Values

be used for the co-primary Hgb analysis.
 
 Some displays may be created for either central laboratory Hgb values only or HemoCue Hgb values only. The central laboratory summary will be considered the primary summary in this case.
Evaluable Hemoglobin Values

 Evaluable Hgb values are on-treatment Hgb values (see Section 10.4.1) that are not taken within the 8 weeks following a red blood cell transfusion, a whole blood transfusion, or a non-randomized ESA treatment which occurs on or after the randomization date. Red blood cell transfusions, whole blood transfusions and non-randomized ESA treatments occurring on or after the randomization date are identified by comparing the start and stop date of the respective transfusion or ESA concomitant medication record to the randomization date.
Imputed Hemoglobin Values

 For each missing value between baseline to Week 52 (inclusive), 200 imputed values will be generated using the multiple imputation method (see Section 7.1.2). The average of these 200 imputed values will be used as the value for this missing value in the summary tables and figures. For co-primary efficacy Hgb analysis and the corresponding subgroup analyses using all available observed and imputed Hgb values (on and off-treatment), Rubin's rules [Rubin, 1987] will be used to combine results of the imputed datasets using SAS PROC MIANALYZE procedure.
EP Hemoglobin Value for Co-primary Hgb Analysis

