10.6.3.3. Time to Rescue

Time to Stopping Randomized Treatment Due to Meeting Rescue Criteria
Meeting Rescue Evaluation Criteria and Rescue Criteria

 Subjects meeting evaluation criteria for rescue are identified from the Rescue Treatment eCRF. Subjects with a record on this form are considered to have met evaluation criteria for rescue. It is possible that a subject could be evaluated for rescue more than once, and in that case a subject would have multiple records on this form. Subjects unable to be evaluated for rescue are subjects who met evaluation criteria for rescue, but were unable to be assessed at the 4 week check (e.g., subjects who died, permanently discontinued randomized treatment or withdrew from the study before the 4 week check). The outcome of initial intervention eCRF field on the Rescue Treatment eCRF will be blank for these subjects. Subjects meeting rescue are identified by the response 'Met rescue criteria' to the outcome of initial intervention question on the Rescue Treatment eCRF.
Event Date

 Treatment stop date when the primary reason and subreason for randomized treatment stop are: 
 Primary reason: Subject reached protocol-defined stopping criteria Subreason: Rescue
General Definitions

 Time to event (days) = date of event – randomization date +1 Censored time (days) = censoring date – randomization date + 1 Rescue person years = (cumulative total time to stopping randomized treatment for subjects

Time to Stopping Randomized Treatment Due to Meeting Rescue Criteria

who stopped randomized treatment due to meeting rescue criteria + cumulative total of censoring time for subjects who did not stop randomized treatment due to meeting rescue criteria) / 365.25
 
 • Rescue incidence rate (per 100 person years) = (100 * number of subjects who stopped randomized treatment due to meeting rescue criteria) / rescue person years • Rescue absolute rate difference (per 100 person years) = daprodustat rescue incidence rate (per 100 person years) – darbepoetin alfa rescue incidence rate (per 100 person years)
Time Period for Treatment Discontinuation

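### A missing or year-only stop date on the last exposure record is imputed as study completion (or 31 December) even when the IP Discontinuation form records an earlier permanent stop

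*SAP*

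**What the plan says.** SAP Section 10.6.1 defines two dates. The last non-zero dose date is the "Date of last actual dose of randomized study treatment from the IP Discontinuation eCRF form". The treatment stop date is "Calculated as the latest randomized treatment dose stop date for subjects who have a non-missing treatment start date". A record with a missing or partial stop date supplies it "if the associated dose start date for that exposure record is on or after the last non-missing randomized treatment dose stop date", which is normally true of a subject's last record.

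The treatment stop date is then imputed as follows:

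- Day missing: the last day of the month, or the study completion/withdrawal date if that is in the same month.
- Day and month missing: 31 December, or the completion/withdrawal date if that is in the same year.
- All missing: "The study completion or withdrawal date will be used only for subjects who have a non-missing treatment start date".

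The IP Discontinuation form also carries an item on permanent discontinuation and a primary reason. Section 10.6.2.1 shows this when it fills them in for subjects without the form: "Was the study treatment stopped permanently before the scheduled end of the treatment period? = Yes", with the reason set to missing. A missing or partial last non-zero dose date is repaired from the treatment stop date. No rule works in the other direction.

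For time to rescue (Section 10.6.3.3), the event date is the "Treatment stop date when the primary reason and subreason for randomized treatment stop are" protocol-defined stopping and rescue. In Section 10.6.3.1, "Evaluable Hgb values are on-treatment Hgb values", less those within 8 weeks after a transfusion or non-randomized ESA.

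**The concern.** Section 10.7.1 says that subjects who stop drug are encouraged to remain in the study, so completion can fall years after the true stop. When the rule is triggered for such a subject, a known date on one form is overridden by a much later one.

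The treatment stop date feeds:

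- exposure (10.6.2.5);
- time to treatment discontinuation (10.6.2.3);
- the rescue event date (10.6.3.3);
- the on-treatment state for Hgb, iron, transfusion and PRO data, which ends one day after the stop date (10.4.1.1).

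BP, laboratory and AE states use the last non-zero dose date instead (10.4.1.3, 10.4.1.4). The same subject could therefore be post-treatment for BP and on-treatment for Hgb at one visit.

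**Working it through.** The SAP gives no figure to reproduce. The check is date arithmetic for one illustrative subject, plus a count of affected visits.

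**Inputs.** Assumed: randomization and first dose on the same day; last dose at Week 30 on the IP Discontinuation form; last exposure record with a wholly missing stop date; study completion at Week 104, 156 or 208. From the SAP: exposure and time to rescue are both end date minus start date plus 1 day. After discontinuation, Hgb is scheduled at Weeks 4, 16, 28, 40 and 52, then every 12 weeks from Week 64 (10.2.1.3).

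**Duration.** Using the form's date: 30 × 7 + 1 = 211 days. Under the SAP rule:

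| Completion | Days under the rule | Ratio to 211 | Excess (years) |
|---|---|---|---|
| Week 104 | 104 × 7 + 1 = 729 | 3.45 | 518 / 365.25 = 1.42 |
| Week 156 | 156 × 7 + 1 = 1093 | 5.18 | 882 / 365.25 = 2.41 |
| Week 208 | 208 × 7 + 1 = 1457 | 6.91 | 1246 / 365.25 = 3.41 |

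A rescue event is kept but dated at completion. A subject can count as rescued only if the stop reason is present, and a subject without the IP Discontinuation form has that reason set to missing. So every rescue event comes with a form on which a last-dose date is requested.

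**Year-only dates.** The error is at most the span from the true stop to 31 December, just under one year.

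**Hgb visits relabelled on-treatment.** In the evaluation period: Weeks 40 and 52. In total:

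- completion at Week 104: Weeks 40, 52, 64, 76, 88 and 100, so 6 visits;
- Week 156: add Weeks 112, 124, 136 and 148, so 10;
- Week 208: add Weeks 160, 172, 184, 196 and 208, so 15.

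Unless the 8-week filter removes them, these values enter the while-on-treatment, responder, time-in-range and evaluable MMRM analyses, each within its own time window.

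**Death.** If a subject who stopped earlier dies on study and the completion date equals the death date, the imputed stop date equals the death date. Section 10.6.2.3 then censors that subject as having died on treatment in the discontinuation summary that excludes such deaths.

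**Number of subjects.** Not given. With 4500 randomized (the design figure in 2.3), and assuming 30% stop early and 0.5% to 2% of their last records lack a stop date: 4500 × 0.30 = 1350; 1350 × 0.005 ≈ 7; 1350 × 0.02 = 27. Both percentages are assumptions. Those stopped for rescue would be only a part of this number.

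**The case against.** The strongest case against is that the reach is small, and most of it stands.

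- **Confirmatory results.** A reader might infer that the co-primary Hgb or MACE result is at risk. It is not. Co-primary Hgb uses on- and off-treatment values (7.1.2). MACE and the principal secondary endpoints use the follow-up period from randomization (10.6.4.1). On-treatment MACE uses the last non-zero dose date plus 28 days, which comes from the IP Discontinuation form when that date is present. Time to rescue is tested only nominally.
- **Per-protocol analysis.** A reader might infer contamination here too. The Week 30 stopper has at most Weeks 28, 40 and 52, that is 3 of 7 scheduled evaluation-period values, and so meets exclusion 02 (fewer than 5 of 7; 10.1.1). Stretching the last record also tends to make it under-compliant (exclusion 03). Only late stoppers could escape both.
- **PRO data.** After discontinuation the instruments are scheduled only at the early discontinuation visit (10.2.1.3), so there is almost nothing to mislabel.
- **Evaluable Hgb.** The 8-week filter still removes values after a transfusion or non-randomized ESA.
- **Rarity.** Database cleaning precedes the freeze (3.2), so such records may be few. That limits frequency, but Section 10.6.1 expects such records and writes a rule for them.
- **Two dates by design.** Zero-dose periods justify a stop date later than the last dose while the algorithm is being followed. They do not justify carrying it to study completion after a recorded permanent stop.
- **Arm neutrality.** Substituting the bare last-dose date would drop the rest of the dosing interval: 27, 13 or 6 days for darbepoetin every 4, 2 or 1 weeks, and 0 days for daily daprodustat. This objection is correct and shapes the fix.

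**Conclusion.** The rule as written gives a wrong date whenever three things coincide: the governing last exposure record has a wholly missing or year-only stop date, the IP Discontinuation form records an earlier permanent stop, and the subject stays in follow-up past it. Nothing elsewhere in the SAP corrects it. The error per subject can be the whole remaining follow-up, 1.42 to 3.41 years in the illustration, or just under one year for a year-only date.

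It affects time to rescue, exposure, time to treatment discontinuation and some evaluable Hgb values. It does not touch the co-primary or multiplicity-controlled analyses, and its effect on PRO and per-protocol results is minimal. The number of affected subjects is unknown, and no shift in a hazard ratio or mean can be calculated from the document. It is a limited derivation defect, worth correcting because the better date is already collected.

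**What to change.** Add to Section 10.6.1: for subjects recorded as permanently discontinued, impute a missing or partial treatment stop date from the last-dose date on the IP Discontinuation form. Extend it to the end of the dosing interval recorded for that last dose, so that darbepoetin every 4, 2 or 1 weeks and daily daprodustat are treated alike, or to the end of any later zero-dose period assigned by the IRT.

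The imputed date should not precede the start of that exposure record, should agree with any known month or year, and should not fall after study completion/withdrawal or death. Use the present rule only if the IP Discontinuation date is also missing.

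The cost is a slightly more complex derivation, specified before unblinding. Dose frequency, IRT assignments and the form are already collected. Reporting how many stop dates were imputed, by arm and by rule, would show whether the issue arose at all.
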